4.2.2 Subsequent Treatment Extension Visits

The following assessments will be performed at each treatment extension visit beyond TE1, unless otherwise specified:

- Assess for any Adverse Events and changes in Concomitant medications (see [section 9](#) and [7.6](#)),
- Neurological assessment (see [section 7.9](#)) [*at EOT2*],
- Symptom-directed physical examination (see [section 7.7](#)),
- Electrocardiogram (ECG) (see [section 7.8](#)) [*at EOT2*],
- Vital Signs (see [section 7.10](#))
 - **Note:** *Post-treatment vital signs will be assessed within 15 minutes following IP administration performed at clinic.*
- Collection of Blood Specimens (see [section 7.11](#)) for
 - Plasma HIV-1 RNA level
 - TruCount T Assay

➢ **Note:** *Occurs once every 4 weeks when subject is at clinic.*

- Complete Blood Count (CBC)
- Biochemistry
- Coagulation indices
- Urinalysis

- **Note:** Occurs once every 12 weeks when subject is at clinic.
- Study Treatment Administration (PRO 140)
- Injection Site Reaction Assessment (see [section 7.13](#))
 - **Note:** To assess injection site reactions, the investigator will use the DAIDS AE grading table (refer to [section 16.3](#)).

4.2.3 Virologic Failure (VF) Visit

Virologic failure is defined as two consecutive HIV-1 RNA levels ≥ 400 copies/mL.

The following assessments will be performed for subjects who experience virologic failure at any time during the Treatment Phase:

- Assess for any Adverse Events and changes in Concomitant medications (see [section 9](#) and [7.5](#)),
- Complete Physical Examination (see [section 7.7](#)),
- Vital Signs (see [section 7.10](#)),
- Neurological Assessment (see [section 7.9](#)),
- Subject-perceived Injection Site Pain Assessment (see [section 7.13](#)),
- Collection of Blood Specimens (see [section 7.11](#)) for
 - Plasma HIV-1 RNA level
 - TruCount T Assay
 - Complete Blood Count
 - Biochemistry
 - HIV Drug Resistance Assay
 - HIV PhenoSense Entry[®] Assay
 - HIV Trofile[®] Assay
- Change in Optimized Background Therapy based on genotypic and phenotypic results obtained at VF visit.

4.3 FOLLOW-UP PHASE

The duration of follow-up depends on whether subject experiences virologic failure.

- Subjects who experience virologic failure within the Treatment Extension Phase will be followed up every 4 weeks until viral suppression is achieved (i.e., plasma HIV-1 RNA levels below level of detection) or up to a maximum of 6 months after cessation of therapy if the treating physician does not feel that there is an antiretroviral regimen that will regain full viral suppression.
- Subjects who do not experience virologic failure at the end of the Treatment Extension Phase, will be followed up every 2 weeks for total of 4 weeks.

4.3.1 Follow-Up Visits

The following assessments will be performed at each follow-up visit, unless otherwise specified:

- Assess for any Adverse Events and changes in Concomitant medications (see [section 9](#) and [7.6](#)),
- Symptom-directed physical examination (see [section 7.7](#)),
- Vital Signs (see [section 7.10](#)),
- Collection of Blood Specimens (see [section 7.11](#)) for
 - Plasma HIV-1 RNA level
 - TruCount T Assay

4.4 UNSCHEDULED VISITS

In the event that the patient returns to clinic at a time other than a regularly scheduled study visit, the visit will be regarded as an unscheduled visit. Assessments at unscheduled visits are at the discretion of the Investigator.

5 SUBJECT COMPLETION AND WITHDRAWAL

5.1 SUBJECT COMPLETION

- A subject who completes the Treatment Extension Phase (without virologic failure) and 4-week Non-Virologic Failure Follow-Up Phase will be considered as having completed the study.
- A subject who experiences virologic failure during the Treatment Extension Phase, undergoes the Virologic Failure (VF) Visit assessments and is followed up until viral suppression is achieved or up to a maximum of 6 months after experiencing virologic failure if the treating physician does not feel that there is an antiretroviral regimen that will regain full viral suppression will be considered as having completed the study.

5.2 SUBJECT WITHDRAWAL

A subject who enters the Treatment Extension Phase but does not complete the study, as defined in [Section 5.1](#), is considered to have prematurely withdrawn from the Study.

All subjects have the right to withdraw at any point during treatment without prejudice to future care. It will be documented whether or not each subject completed the clinical study. If for any subject, study treatment or observations were discontinued, the reason(s) will be recorded.

The Investigator can discontinue a subject at any time if it is considered medically necessary.

In addition, subjects WILL be withdrawn from the study, in consultation with the Medical Monitor and the Investigator, if any of the following are met:

- A subject is significantly non-compliant with the requirements of the protocol.
- The investigator determines that it is in the best interest of the subject.
- Subject chooses to withdraw or is withdrawn due to an adverse event
- A subject becomes pregnant

Note: *The pregnancy will be followed to term for safety follow-up. Relevant safety information collected after the study has completed will be reported as supplemental information.*

- Discontinuation of study by Sponsor

Premature withdrawal from the study MAY occur if, in consultation with the Medical Monitor and the Investigator, any of the following are met:

- A subject is treated with a prohibited medication.

- Major protocol violation

5.2.1 Discontinuation of Study Treatment

Discontinuation of study treatment (PRO 140) and continuation of HAART as per standard of care is recommended if:

- Subject experiences virologic failure, defined as two consecutive HIV-1 RNA levels ≥ 400 copies/mL

Note: Subjects will be allowed to continue PRO 140 with existing OBT regimen while waiting for new regimen to be constructed by the Investigator.

- Develops AIDS-defining conditions as specified in Appendix I ([Section 16.1](#)) under which subject is unable to continue treatment with study drug (PRO 140), or subject require treatment with prohibited concomitant medications.
- Shows signs or symptoms of clinically significant immunosuppression
- Subject or the subject's clinician wishes to adjust OBT (except in the event of toxicity management).
- Subject becomes pregnant.

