1.6.1.4 Pregnancy

Risks to unborn babies are unknown at this time; pregnant females will be excluded from this study. Females of childbearing potential must have a negative pregnancy test prior to enrollment. Both male and female patients and their partners of childbearing potential must agree to use appropriate birth control methods throughout the study duration (excluding women who are not of childbearing potential and men who have been sterilized).

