3 STUDY DESIGN

This is an extension study, to provide continued access to PRO 140 to subjects who complete participation in PRO140_CD02 or CD02_OpenLabel and continue to receive clinical benefit and would require PRO 140 to form a viable regimen, in the opinion of the treating physician. The patient population for this trial is treatment-experienced HIV-infected patients with CCR5-tropic virus who demonstrate evidence of HIV-1 suppression after successfully completed 24 weeks of treatment in the PRO140_CD02 or CD02_Open Label study.

Subjects participating under Protocol versions 1.0-3.0 received 350 mg of PRO 140. Dose was increased from 350 mg to 700 mg weekly to provide maximum viral load suppression in a heavily treatment experienced population to avoid developing resistance to current OBT therapies.

Those that were enrolled under version 1.0-3.0 have the option of remaining on their current dose of 350mg or increasing their dose to 700 mg for the remainder of the trial.

The study is divided into three phases: Screening, Treatment Extension and Follow-up.

Screening Phase begins with signing of Informed Consent and lasts up to 21 days. All subjects will continue taking PRO 140 SC injection in addition to OBT during the Screening Phase.

Subject will enter the Treatment Extension Phase as soon as HIV-1 viral load results are available for review by Investigator. Treatment Extension Phase consists of weekly study treatment injections along with OBT. Study participants will be regularly monitored for viral load and will cease weekly study treatment injections should they experience virologic failure. Virologic failure is defined two consecutive HIV-1 RNA levels ≥ 400 copies/mL.

Note: Subjects will be allowed to continue PRO 140 with existing OBT regimen while waiting for new regimen to be constructed by the Investigator.

Subjects who experience virologic failure at any point during the Treatment Extension Phase will undergo the Virologic Failure (VF) Visit assessments and will be followed up every 4 weeks until viral suppression is achieved (i.e., plasma HIV-1 RNA levels below level of detection) or up to a maximum of 6 months after cessation of therapy if the treating physician does not feel that there is an antiretroviral regimen that will regain full viral suppression. Subjects who do not experience virologic failure, will be followed up every 2 weeks for total of 4 weeks.

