4 STUDY SCHEDULE

This study is divided into three phases: Screening, Treatment and Follow-up.

(1) **Screening Phase:** This phase lasts up to 21 days and begins with signing of Informed Consent. Assessments performed during this phase determine the subject's final eligibility for study participation. Subjects who meet all eligibility criteria will receive first treatment injection at Treatment Extension Visit 1 (*which corresponds to EOT from PRO140_CD02 or CD02_OpenLabel study*).

All subjects will continue taking PRO 140 along with OBT during the Screening Phase.

Note: Subject consent and screening assessments should be completed prior to EOT visit in the PRO140_CD02 or CD02_OpenLabel study.

(2) **Treatment Extension Phase:** Subjects will receive weekly treatments (window period of ± 3 days) until virologic failure is experienced, consent is withdrawn, the study drug is approved, or the trial is completed/ended by CytoDyn, whichever comes first.

Virologic failure is defined as two consecutive HIV-1 RNA levels ≥ 400 copies/mL.

Subjects who meet all eligibility criteria will receive first treatment injection at Treatment Extension Visit 1 (*which corresponds to EOT from PRO140_CD02 or CD02_OpenLabel study*).

PRO 140 will be administered by a qualified medical professional (MD, DO, PA, LPN, LVN, NP, RN, or CMA if permitted by state law) or self-administered by subjects.

Any time during the Treatment Extension Phase, if virologic failure occurs, Investigator will readjust antiretroviral regimen based on HIV-1 genotypic and/or phenotypic drug resistance results obtained during the VF visit.

Subjects will be allowed to continue PRO 140 with existing OBT regimen while waiting for new regimen to be constructed by the Investigator.

(3) **Follow-Up Phase:** The duration of follow-up depends on whether or not subject has experienced virologic failure during the Treatment Extension Phase.

- Subjects who experience virologic failure within Treatment Extension Phase will be followed up every 4 weeks until viral suppression is achieved (i.e., plasma HIV-1 RNA levels below level of detection) or up to a maximum of 6 months after cessation of therapy if the treating physician does not feel that there is an antiretroviral regimen that will regain full viral suppression.
- Subjects who do not experience virologic failure at the end of Treatment Extension Phase, will be followed up every 2 weeks for total of 4 weeks.

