4.2 TREATMENT EXTENSION PHASE

Treatment Extension Phase begins with an evaluation of viral load–results collected during the Screening Phase. Subjects who meet all eligibility criteria, as per data gathered from Screening

Phase are to be treated. All subjects who fail to meet eligibility criteria will be considered screen failure and exit the study without further evaluation.

As shown in [Table 4-3](#), eligible subjects will receive weekly treatment injections (\pm 3 days) until virologic failure or another reason for discontinuation, occurs, whichever occurs first. Eligible subjects will receive PRO 140 700mg* administered as two subcutaneous injections along with Optimized Background Therapy (OBT).

Note: Subjects enrolled prior to Protocol v4.0 may still be receiving the original 350mg dose and have the option of increasing their dose to 700mg.

Table 4-3: Treatment Extension Phase [PRO 140 + OBT]

Study Drug	Dosage Form	IP concentration	Dosing Frequency and Amount	Route of Administration
PRO 140	Parenteral solution	175 mg/mL	2 injections of PRO 140 (2 X 2 mL/inj.) per week	SC injection

The study treatment (PRO 140 SC injections) will be administered by a qualified medical professional (MD, DO, PA, LPN, LVN, NP, RN, or CMA if permitted by state law) or self-administered by subjects depending on the study visit week.

All study subjects will continue their current Optimized Background Therapy:

- Throughout the Treatment Extension Phase, or
- Anytime during the Treatment Extension Phase, if virologic failure occurs or have met any other criteria for discontinuation of study treatment as specified in [section 5.2.1](#) of the protocol. Subjects will be allowed to continue PRO 140 with existing OBT regimen while waiting for new regimen to be constructed by the Investigator.

Note:

- Subjects may return to clinic for an additional blood draw in-between the clinic visits for plasma HIV-1 RNA or CD4+ levels, per the discretion of the Investigator.
- Subjects who experience virologic failure at any time during the Treatment Extension Phase will undergo the Virologic Failure (VF) Visit assessments and enter the Follow-up Phase of the study.
- Subjects who meet any criteria (other than virologic failure) for discontinuation of study treatment as specified in [section 5.2.1](#) of the protocol, will undergo End of Treatment

Extension Phase (EOT2) Visit assessments and enter the Follow-up Phase of the study.

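### Section 5.2.1 only recommends stopping PRO 140 at virologic failure and at pregnancy, while other sections direct a stop, follow-up or study withdrawal for the same events

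*Protocol*

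**What the plan says.** Protocol Section 5.2.1 governs discontinuation of study treatment. Its lead-in is advisory: "Discontinuation of study treatment (PRO 140) and continuation of HAART as per standard of care is recommended if". Virologic failure and pregnancy are both in the list that follows.

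For virologic failure, Section 3 is directive: subjects "will cease weekly study treatment injections should they experience virologic failure". Section 4 runs weekly treatment "until virologic failure is experienced, consent is withdrawn, the study drug is approved, or the trial is completed/ended by CytoDyn, whichever comes first", and Section 4.2 runs it "until virologic failure or another reason for discontinuation, occurs, whichever occurs first". Protocol Section 8.1 and SAP Section 2.3.1 also list failure as an event that ends weekly dosing. A bridging note appears in Section 3 and again in Section 5.2.1: "Subjects will be allowed to continue PRO 140 with existing OBT regimen while waiting for new regimen to be constructed by the Investigator".

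For pregnancy, Section 5.2 says "subjects WILL be withdrawn from the study, in consultation with the Medical Monitor and the Investigator, if any of the following are met", and one of the listed conditions is "A subject becomes pregnant". A separate list in the same section covers cases where withdrawal only may occur. Section 1.6.1.4 states: "Risks to unborn babies are unknown at this time; pregnant females will be excluded from this study".

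Section 4.2 refers to Section 5.2.1 for the discontinuation criteria and then directs what follows. Subjects with virologic failure have the VF visit and enter the Follow-up Phase. Subjects meeting any other Section 5.2.1 criterion, which includes pregnancy, have the EOT2 visit and enter the Follow-up Phase.

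**The concern.** A site facing either event has to know two things: whether PRO 140 must stop, and whether the subject stays in the study. The protocol answers each in more than one way. Section 4.2 names Section 5.2.1 as the source of the discontinuation criteria, so the softest wording sits where a site is told to look. Two sites could each follow a passage faithfully and still handle the same event differently.

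At stake is mainly subject safety and consistent conduct. For pregnancy the issue is fetal exposure to a product whose fetal risk the protocol says is unknown. For virologic failure it is whether dosing beyond the bridging period is ruled out or merely advised against.

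**Working it through.** No arithmetic applies. The check sets every passage on stopping PRO 140 at these two events side by side.

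| Place | Virologic failure | Pregnancy |
|---|---|---|
| Protocol 3 | Injections stop; bridging note | Not addressed |
| Protocol 4 | Ends weekly treatment; bridging note | Not addressed |
| Protocol 4.2 | Ends weekly injections; VF visit, then Follow-up; bridging note | Falls under the other 5.2.1 criteria: EOT2 visit, then Follow-up |
| Protocol 5.2 | Not a withdrawal criterion | Withdrawal from the study is mandatory |
| Protocol 5.2.1 | Treatment stop is advisory; bridging note | Treatment stop is advisory; no bridging note |
| Protocol 5.2.2 | Remaining in the study is suggested for everyone, on or off treatment | Same |
| Protocol 8.1, SAP 2.3.1 | Ends weekly dosing | Not listed |

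**Virologic failure.** The bridging note is the obvious candidate to reconcile Section 3 with Section 5.2.1. It cannot, because it stands in both sections and so does not account for the difference between them. It covers only the wait for a new regimen. After that wait, Section 3 requires that PRO 140 has stopped and Section 5.2.1 advises it.

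The note also fits poorly with Section 4.2. A failing subject moves to the Follow-up Phase, but the follow-up schedule in Table 4-2(b) has no PRO 140 row. A subject still receiving bridging doses is therefore in a phase whose schedule provides for none.

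**Pregnancy.** There are three instructions. Section 5.2 takes the subject out of the study. Section 4.2 keeps the subject in the study, off treatment and in follow-up. Section 5.2.1 recommends stopping treatment and does not mention study status. Section 5.2.2 leans towards keeping the subject in the study.

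The phrase in Section 5.2 about consulting the Medical Monitor and the Investigator does not soften the mandatory list, because the same phrase introduces the optional list. The authors distinguished required from discretionary withdrawal in that section and placed pregnancy among the required cases.

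**Precedence.** No passage says which section governs when they differ.

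**The case against.** The strongest reply is that one advisory word is surrounded by directive text. Section 4.2, which points to Section 5.2.1, itself says what must happen next for both events. The bridging note sits directly under the virologic failure item in Section 5.2.1. If the advisory lead-in already let a site continue at will, a note permitting continuation while a regimen is built would be needless, so the natural reading is a stop with a limited exception. On pregnancy, study withdrawal and treatment discontinuation are different acts: withdrawing the subject satisfies Sections 5.2 and 5.2.1 together, and nothing in Section 5.2.1 permits dosing in pregnancy.

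Much of this stands, and it limits the consequences. It does not remove the conflict. Inferring a mandatory stop from context still leaves the discontinuation section worded as advice. Withdrawing a pregnant subject under Section 5.2 also does not deliver what Section 4.2 directs, which is follow-up within the study.

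Three stronger readings are tempting, and the documents do not support them.

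- A reader might infer that dosing after failure has no upper limit. Section 4.2 moves failing subjects out of the open-ended phase and into Follow-up, which has no scheduled PRO 140 and ends at viral suppression or after at most 6 months.
- A reader might infer that the viral-load and CD4 outcomes are biased. SAP Sections 7.2.1 and 7.2.2 plan descriptive summaries by time point during treatment, and no summary has been shown to change.
- A reader might infer that failures cannot be coded under the withdrawal-criteria deviation in SAP Section 7.1.2. Virologic failure is not a Section 5.2 withdrawal criterion, and Section 5.1 counts failing subjects who finish follow-up as completers, so that category is not shown to apply to them.

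**Conclusion.** The inconsistency is real. At virologic failure, a directive in Section 3, supported by four other passages (Protocol Sections 4, 4.2 and 8.1 and SAP Section 2.3.1), meets a recommendation in Section 5.2.1. At pregnancy, three passages give three instructions that differ in force and in what becomes of the subject's place in the study. Pregnancy is the more serious of the two, because of the stated unknown fetal risk and because no bridging exception narrows the gap.

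The size cannot be calculated. The protocol plans up to 50 subjects and gives no expected number of failures or pregnancies; there may be few of either. The conclusion rests on the wording alone and assumes that a site might follow any one of the passages, since none is given priority. It does not claim that any site has continued dosing. It takes no view on which clinical rule is right. The passages should be reconciled because they are operative stopping rules that bear on subject safety.

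**What to change.** Reconcile the lead-in of Section 5.2.1 with Protocol Sections 3, 4, 4.2, 5.2 and 8.1. For each of the two events, state one status (mandatory or advisory) and one consequence (withdrawal from the study, or treatment stop with follow-up), and use the same statement everywhere. Say how the bridging note fits with entry into the Follow-up Phase after failure, given that the follow-up schedule has no PRO 140 row. Check that SAP Section 2.3.1 still matches the agreed wording. Which rule applies is for the sponsor and its clinical advisers to decide.

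The cost is a wording amendment to a few protocol sections, with a matching SAP line if needed. It adds no visits, assessments or analyses.

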5.2.2 Data Collected for Withdrawn Subjects

Patients may withdraw from the study or discontinue study treatment at any time; however, CytoDyn is dedicated to minimizing missing data in this study. It is therefore suggested that all patients, regardless of whether they continue to receive study treatment, continue within the study.

Investigators considering discontinuing study treatment should contact the medical monitor prior to such discontinuation. Patients who have study treatment discontinued will continue to be followed, per protocol, whenever possible. Patients who have study treatment discontinued due to a serious adverse event will be followed until resolution or stabilization of the event.

In the event that a subject is withdrawn from the study at any time due to an adverse event or serious adverse event (SAE), the procedures stated in [Section 9.1.1](#) or [9.3](#), respectively must be followed.

Every attempt should be made to collect follow-up information. The reason for withdrawal from the study will be recorded in the source documents and on the appropriate page of the eCRF.

Before a subject is identified as lost-to-follow up, the site should make all reasonable efforts to contact the subject. These attempts must be documented and should include at a minimum one phone call and one certified letter.

